## RISKS

The possible **risks**, exactly as described in the consent form, include the following:

*Loss of Confidentiality:* Once others know that you are participating in the study, you may lose some confidentiality. Fire crews work in close quarters and some spend time living together in the fire house, so confidentiality may be lost by your presence at the testing appointments. We will reduce this risk because your name will not be on any documents and your personal data will not be shown to anyone during the test sessions.

*Depression, Anxiety, and Stress Scales (DASS-21):* The risk associated with completing this short 21-item survey is that you may feel uncomfortable while answering the questions. If you feel this and your symptoms are severe, we will work with you to refer you to a proper clinician who is part of your health network.

*Blood glucose, cholesterol, and blood draw:* These measurements will involve a finger prick and a needle stick. The risks associated are slight discomfort in the site. These are routine and conventional procedures used to measure blood levels of metabolites. Minor risks include a small amount of bleeding under the skin (bruising), but this has been reported in <10% of the cases, dizziness, and a very small risk of infection (1 in 1000). The risk of infection will be reduced by proper cleaning and antiseptic techniques by the technician.

*Blood vessel studies:* The blood vessel ultrasound studies may include discomfort in the arm and leg when the cuff squeezes to take a measurement. This feeling could be similar to what is felt when a foot or leg falls asleep after sitting in certain positions. This is not a risk to your health, but it is a discomfort. To help with this risk, we recommend that you stay very still and as the blood flows back to the arm and the feeling will go away.

*Fitness testing/training:* The risk of any exercise is injury to muscles, joints, ligaments, and tendons. It has been found that in 1 out of every 70,000 exercise tests, a person could die from heart problems. In medical terms, doctors call this a rare event. Because you are otherwise healthy with no known risk factors, the risks of a medical problem are even lower. You are aware that if any exercise makes you uncomfortable, you should notify us immediately.

*Diet intervention:* The risk of allergy exists when any special diet is followed. You are asked in your initial Wellness questionnaire if you have any known food allergies and this is documented in the inside of your folder. If you do have allergies, a modified diet will be provided to you. If something arises, please notify HEART lab staff immediately.

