### Brief protocol summary:

Study participants from both groups (firefighters & civilians) will be enrolled for a total of about 8 weeks. During this time period they will complete the following steps:

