### **Orientation & Consent**

Study participants will learn about the study, have questions answered and review the consent form. They will complete the wellness questionnaire.

They will also complete a short 21-item scale that asks questions related to their feelings over the past week. One of the main components of blood pressure is emotional response, so for this study we will also assess participants stress and anxiety levels with the Depression, Anxiety, and Stress Scales (DASS-21) scale. The DASS-21 is a 21-item self-reported scale that will determine the presence and severity of the three listed psychometric characteristics above.

The reliabilities of the DASS-21 (internal consistencies) Anxiety, Depression, Stress, and Total scales are 0.88 (95% CI = 0.87-.89) for the Depression scale, 0.82 (95% CI = 0.80-.83) for the Anxiety scale, 0.90 (95% CI = 0.89-.91) for the Stress scale, and 0.93 (95% CI = 0.93-.94) for the Total scale.

The DASS-21 may be administered and scored by non-psychologists, and none of the items refers to suicidal tendencies. The primary function of the DASS-21 is to assess the severity of symptoms of depression, anxiety and stress. Since the scale was developed with non-clinical samples, it is suitable for even adolescents and adults, so can be considered low risk. Despite it being low risk, a comment has been placed in the Risk section of the consent form that states: "The risk associated with completing this short 21-item survey is that you may feel uncomfortable while answering the questions. If you feel this and your symptoms are severe, we will work with you to refer you to a proper clinician who is part of your health network."

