### **Pre-Intervention Testing Visits**

All participants will complete three testing components during pre-intervention. This includes a morning ***fasted study***, a ***blood pressure monitoring***, and a ***fitness test***. We coordinate these appointment times to fit into participant's schedule.

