#### ***Fasted Testing Appointment:***

The total time for this visit will be around 45 minutes. ***This test will occur on UNH campus in NH Hall.*** They will be required to fast for 10 hours before coming into the lab for the testing. For this visit, we ask that they avoid food or drink (water is allowed) for at least 10 hours before coming into the lab. We also ask that they avoid alcohol and exercise the night before. Height, weight, and blood pressure will be taken. Body composition will be measured, glucose and cholesterol levels measured, a blood draw collected, and blood vessel ultrasound and pressure studies will be done.

***Considering that the population is seemingly healthy based on other exclusion criteria, it is still possible to identify high blood pressure or high lipid/glucose levels in the participants. This would not be an exclusion from the study. If this occurs, we inform them and offer to provide them with the data, if they wanted to follow-up with their physician.***

**Body composition test** will tell the investigators what percentage of the body is fat, muscle and bone. The instrument that measures body composition is called bioelectrical impedance (BIA). The machine will cause a very small current to travel through the body for 2-3 seconds, but nothing will be felt. To do this test, they will lie on a table on their back with left foot exposed. To collect the measurements, a technician will place two electrodes on the left foot and two electrodes on left hand.

**Blood glucose and cholesterol measurements** will tell the investigators what the levels of fasted plasma glucose and cholesterol are. We will be measuring these with a finger-prick test. Only one finger prick will occur, and a single large drop of blood will be collected.

**Plasma inflammation, oxidative stress, and vasodilation levels.** A blood draw will occur where we collect 2 tubes of blood (equivalent of 7 tsp or 1.2 oz). This will allow us to measure common markers that circulate in the blood which are related to heart health.

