## **DATA**

Data will be deidentified in study database and when shared with the sponsor. All participants will be assigned an ID code upon entry into the study. All data collection forms will have this ID number listed, with no identifying information at all on the data sheets. We will keep all documentation safely locked in a locked office, in a locked file cabinet. All data points will be entered based on the ID number, and all data will be stored on UNH Box. Only the PI and students affiliated with the study will have access to the data and any data kept on Box will be deidentified.

Data will be aggregated and presented in publications and presentations.

The only form with identifying information will be the Health History form. Upon study completion, any identifying information will be destroyed by shredder. As the study is sponsored by the American Heart Association, the approved data plan states that data will be made available through clinicaltrials.gov.

Our interest is in estimating the effect of exercise and diet on the change in blood pressure surge and examine whether it differs between groups. Quantitative analysis will be done. Data will be expressed as mean  $\pm$  the standard deviation, and statistical analyses will be performed using SPSS. The distribution of all variables will be examined using the Shapiro-Wilk test of normality. Repeated measures ANOVA will examine whether any condition by time interaction effects exist. Post-hoc within-group analysis will be performed using paired t-tests to compare values between time-

points. Between group analyses will be performed using independent t-tests to determine if there were significant differences between the firefighter and civilian test groups at each time-point. Pearson correlation will determine if there are relationships between variables, which will be further examined by linear regression analysis.

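### The only stated response to the DASS-21 requires discomfort with the questions as well as severe symptoms, so a severe score alone prompts no stated action

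*Combined protocol and SAP*

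**What the plan says.** The DASS-21 appears in two places: Orientation & Consent, and RISKS.

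- **Purpose.** Orientation & Consent says: "The primary function of the DASS-21 is to assess the severity of symptoms of depression, anxiety and stress".
- **Who scores it.** The same section says: "The DASS-21 may be administered and scored by non-psychologists, and none of the items refers to suicidal tendencies". It gives no severity cut-off and does not say when the form is scored.
- **Response.** The section introduces the consent wording with "Despite it being low risk, a comment has been placed in the Risk section of the consent form that states". That wording, repeated under RISKS, first names discomfort while answering as the risk of the survey. It then continues: "If you feel this and your symptoms are severe, we will work with you to refer you to a proper clinician".
- **Place in the schedule.** The form is completed at orientation. It is not part of the fasted, blood pressure or fitness sessions that follow, which the plan introduces with "All participants will complete three testing components during pre-intervention".
- **Other incidental findings.** Under Fasted Testing Appointment, for high blood pressure or high lipid or glucose levels, the plan says: "If this occurs, we inform them and offer to provide them with the data, if they wanted to follow-up with their physician".

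**The concern.** Discomfort with a questionnaire and severity of symptoms are different things. A person can answer 21 items without unease and still report severe depression, anxiety or stress. If staff follow the sentence as written, that person is offered nothing, although the study holds an answer sheet that would show the problem. A participant with high cholesterol in the same study is told simply because the result is high. The protocol gives no reason for requiring discomfort as well.

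What is at stake is a modest matter of participant safety. The DASS-21 is named in none of the specific aims and in no stated analysis, so no endpoint, comparison or sample-size argument depends on this point.

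**Working it through.** No arithmetic applies. The check is a reading of the two DASS-21 sections, followed by a search of the rest of the text for any other rule that would cover a severe score.

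**Step 1: what 'this' refers to.** In both places the preceding sentence names a single feeling, being uncomfortable while answering. The referral condition is therefore discomfort and severe symptoms, joined by 'and'.

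**Step 2: the condition set out case by case.**

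| Discomfort while answering | Severe symptoms | Stated response |
|---|---|---|
| Yes | Yes | Help with referral |
| No | Yes | None |
| Yes | No | None |
| No | No | None needed |

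The second row is the gap. The third row is reasonable as it stands: discomfort alone need not lead to a clinician.

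**Step 3: does the gap depend on what 'symptoms' means?** The term is not defined.

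- If it means the depression, anxiety and stress symptoms that the scale measures, the table applies directly.
- If it means distress brought on by the survey, the sentence does not address the score at all.

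On both readings, a severe score without discomfort has no stated response.

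**Step 4: does another section fill the gap?**

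- Fasted Testing Appointment has the only rule triggered by a result. It covers blood pressure, lipids and glucose, and it belongs to a different visit.
- BENEFITS hopes that participants will learn about their health and fitness. It is general, not guaranteed and not tied to the DASS-21.
- DATA describes coding and storage, not the return of results.

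**Step 5: size.** The number of participants in the second row would be the sample size, times the proportion with a severe score on any subscale, times the proportion of those who felt no discomfort. The text gives none of the three, so no count or range is offered.

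**The case against.** The strongest objection is that a risk disclosure is being read as an operating procedure. The sentence tells participants about one risk of filling in the form and the help on offer if that risk occurs. It does not say what staff must do with scores, and it does not forbid them to act. This stands in part. A reader might infer that the protocol withholds referral from calm participants with severe scores; the documents do not support that. They support only that no commitment is stated.

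A second objection is that the text is incomplete. A section between the post-intervention visits and DATA is absent, as are the consent pages, and either could say more. That limits the claim to the text available. RISKS does, however, present its wording as exactly that of the consent form, so the joined condition is the plan's own account of what participants are told.

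A third objection is that the plan calls the survey low risk and notes that no item refers to suicidal tendencies. Neither statement is disputed. Low risk from answering is a separate matter from what to do with a severe answer.

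A reader might also infer a long delay before a severe score is seen, because participants "will be enrolled for a total of about 8 weeks", or infer that identifying information could be destroyed before anyone acts. Both inferences rest on late scoring. The documents do not say when the form is scored, and it may be scored on the day. No delay is claimed here.

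Finally, the rule for blood pressure, lipids and glucose promises only to inform participants and offer them the data, so it is not a precedent for same-visit scoring or for referral. That is fair, and orientation is allotted only 15 to 30 minutes. Scoring before the participant leaves is therefore not required in the fix below. The referral offer does not come from that rule; it is the one the plan already makes for the DASS-21.

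**Conclusion.** The point holds within limits. In the text available, the only stated response to the DASS-21 depends on discomfort as well as severe symptoms, and a severe score without discomfort prompts nothing. The plan handles high blood pressure, lipids and glucose differently, on the result alone.

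The change is worth making because it is cheap and the benefit, though modest, falls directly on participants. It has no effect on the aims or the analysis. The number who would benefit is unknown and may be zero.

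The conclusion assumes that the absent section and consent pages contain no further commitment on DASS-21 scores, and that staff follow the sentence as written. If either assumption fails, what remains is a clarification of wording.

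**What to change.** 1. Have existing study personnel score the DASS-21 promptly, at orientation or at the latest before the participant's next study visit. The protocol already accepts scoring by non-psychologists.
2. Write the scale's severe-range cut-off for each of the three subscales into the protocol. The text available gives none.
3. Treat a severe-range score on any subscale as sufficient on its own. Inform the participant privately, away from other crew members, and make the referral offer already promised. Do not make discomfort alone a trigger for referral.
4. In Orientation & Consent, RISKS and the consent form, replace the opening condition of the sentence with 'If your symptoms are severe, whether or not you feel uncomfortable answering,' and leave the promise of referral that follows unchanged.
5. Keep the scored form under the ID code, in line with the DATA section: "All data collection forms will have this ID number listed, with no identifying information at all on the data sheets".

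The cost is a few minutes of scoring per participant, some additional private conversations whose number cannot be computed from the text, three cut-offs added to the protocol, and one changed sentence in the protocol and consent form. No extra staff or study visits are needed.

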## [name] 2020 PROJECT OUTLINE: IRB #8242

### INTRODUCTION

Global hypertension rates have reached epidemic proportions with upwards of one billion individuals diagnosed and estimates that 1/3 of the global adult population is hypertensive. Blood pressure (BP) is a primary risk factor for cardiovascular disease. There are over a million firefighters in America, and firefighting is one of the most hazardous and dangerous jobs with an inherent increased risk of death, just by nature of the work. In fact, many firefighters have hypertension, and cardiac-related incidents are the leading cause of death among firefighters. Also, BP control remains an issue in firefighters, with close to 74% of hypertensive firefighters not having adequate control of their BP. Research that examines BP in firefighters is scarce, and quantifying the BP surge that occurs with pager activation has never been done.

It is known that exercise training improves cardiovascular health, lowers lipid levels, reduces inflammation, and reduces BP. Yet, it is interesting that the National Fire Protection Agency (NFPA) does not require fire companies to have fitness testing or programming for the crew. The NFPA has established that the demands of firefighting require a fitness level of a  $VO_{2\text{max}}$  equivalent of 42 ml/kg/min. Yet, only 20% of volunteer firefighters meet this fitness threshold. And, even worse is that <30% of fire stations have a fitness program or fitness monitoring as part of their standard operating procedures.

It is also known that a healthy diet improves cardiovascular health, lowers lipid levels, reduces inflammation, and reduces BP. Evidence suggests that the Mediterranean diet can improve cardiovascular health, and the Mediterranean diet has been touted the top heart-healthy diet for 2 years in a row. The diet includes a high consumption of fruits and vegetables, a moderate consumption of fish, nuts, low-fat diary, and wine, and a low consumption of red meat and other meat products. Dietary patterns like this reduce inflammation and improve vascular function, which will benefit firefighters. Firefighters know that diet is important, yet they don't know how to modify their diet. Importantly, a recent survey study done at Harvard found that the Mediterranean diet is one that firefighters actually would prefer.

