## **RESEARCH PROTOCOL**

This study is a pre-post exercise and diet intervention study with 2 groups: firefighters and civilians. For the study, firefighters will be recruited from local fire departments and civilians will be recruited from the surrounding areas. The only compensation will be for parking while they are on campus for testing appointments. A study description document is attached which will be used to supplement the word-of-mouth advertising done by walking into local firehouses.

The population is seemingly healthy and low-risk, so physician referral or approval is not needed. Criteria for inclusion: adult 18 years of age and older; no history of renal disease, diabetes, or cardiovascular incident requiring surgery; no existing orthopedic issues that preclude exercise; no more than one anti-hypertensive or cholesterol medication.

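### The consent risk text tells every participant they have no known risk factors, yet eligibility admits people treated for high blood pressure or high cholesterol

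*Combined protocol and SAP*

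**What the plan says.** The RISKS section introduces its content as "exactly as described in the consent form". Under fitness testing and training it gives a figure of one cardiac death per 70,000 exercise tests, then adds: "Because you are otherwise healthy with no known risk factors, the risks of a medical problem are even lower". The sentence is addressed to every signer.

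The RESEARCH PROTOCOL section sets eligibility. On medical history it requires "no history of renal disease, diabetes, or cardiovascular incident requiring surgery". It also rules out orthopedic problems that prevent exercise. On drugs the limit is "no more than one anti-hypertensive or cholesterol medication". On medical clearance it states: "The population is seemingly healthy and low-risk, so physician referral or approval is not needed".

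The INTRODUCTION says blood pressure "is a primary risk factor for cardiovascular disease" and that "many firefighters have hypertension, and cardiac-related incidents are the leading cause of death among firefighters". SPECIFIC AIMS lists clinical blood pressure and lipid levels among the measures by which the study will assess cardiovascular risk.

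**The concern.** The reassurance comes directly after the statement about cardiac death during exercise testing, and it rests on a fact about the reader that the eligibility criteria do not guarantee. Someone taking a drug for hypertension or high cholesterol has a known risk factor on the protocol's own terms, yet is told there is none and that the risk is lower for that reason.

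What is at stake is the accuracy of a cardiac-risk disclosure made before exercise. Participants go on to fitness tests and a six-week circuit programme of about 45 minutes, three times a week, which they do on their own and self-report. The circuit includes a 40 lb carry and 3-minute stair bouts. The point is one of informed consent; endpoints and analysis are not touched.

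**Working it through.** No calculation decides this point. It is a check of one section against another.

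1. **What the consent text asserts.** "Because you are otherwise healthy with no known risk factors, the risks of a medical problem are even lower" makes a factual claim (no known risk factors) and draws a conclusion from it (an even lower risk). The opening word makes the conclusion depend on the claim. Nothing in the RISKS section limits the sentence to a subgroup.

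2. **Who can sign.** Under "no more than one anti-hypertensive or cholesterol medication", a person on one such drug is eligible. The exclusions in RESEARCH PROTOCOL are renal disease, diabetes, certain cardiovascular incidents and orthopedic limits. Hypertension and high cholesterol are not among them.

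3. **Whether these conditions are risk factors in this protocol.** They are. The INTRODUCTION says blood pressure "is a primary risk factor for cardiovascular disease", and SPECIFIC AIMS uses blood pressure and lipids to measure cardiovascular risk.

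4. **Putting 1 to 3 together.** For a participant treated for hypertension or high cholesterol, the factual claim is false at signing, so the conclusion loses its support. The same holds for someone with diagnosed but untreated hypertension, since the criteria limit drugs and not diagnoses.

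5. **Whether the case is foreseeable.** The drug limit itself shows that treated people were expected. Firefighters are one of the two groups, and the INTRODUCTION says hypertension is common among them.

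6. **Whether anything supplied corrects the sentence.** Physician approval is waived. The health history questionnaire is completed at the consent step, but no section links it to different risk wording. The fasted testing section keeps participants with high readings in the study and offers them their data, without any revised risk statement.

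**Number affected.** The documents give no enrolment figure and no share on treatment. If 5%, 15% or one third of participants were under treatment at signing, the count per 100 enrolled would be:

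- 0.05 × 100 = 5
- 0.15 × 100 = 15
- 1/3 × 100 ≈ 33

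These lines only restate their assumptions. The one third is borrowed from the INTRODUCTION's "estimates that 1/3 of the global adult population is hypertensive". That figure is for all hypertension, treated or not, it leaves out cholesterol, and it is not an estimate for this sample.

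**The case against.** The strongest reply is that a false reason does not establish a wrong risk. The documents do not say which population the 1 in 70,000 describes. If it includes people with cardiac disease, this sample, with its exclusions, could sit below it even when one controlled condition is present. Nor do the INTRODUCTION and SPECIFIC AIMS address acute risk during exercise. This stands: the documents do not show that the risk is understated, only that the stated reason is untrue for some signers.

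Second, the consent form was not supplied, and a qualification may appear elsewhere in it. That cannot be checked. The RISKS section nevertheless presents this text as the form's own wording, and nothing supplied qualifies it.

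Third, there are safeguards:

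- The investigator explains the study face to face and answers questions.
- The health history gives staff a chance to notice medication.
- Willingness to continue is asked again at each lab visit.
- High readings are disclosed to the participant.
- The treadmill test is submaximal, the stair climb test lasts 2 minutes, and the plank, wall sit and balance tests also end when position or balance is lost.
- Participants are told to report discomfort.

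These limit the consequences. None changes the sentence in the copy the participant signs and keeps.

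Fourth, a treated condition may be well controlled. A controlled condition is still a known one, and the INTRODUCTION puts inadequate control at close to 74% of hypertensive firefighters.

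Finally, a drug is not a diagnosis. Someone taking one for another reason would not make the sentence false, and neither would a high reading first found at pre-testing, after consent. Both limits are accepted.

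**Conclusion.** The concern holds. The consent risk text and the eligibility criteria contradict each other for participants known at signing to have hypertension or high cholesterol, including those treated with the one permitted drug. For them the premise is false and the lower risk is unsupported.

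The number affected is unknown, and so are the direction and size of any error in the risk itself. The 1 in 70,000 figure is not disputed. The conclusion assumes that the RISKS section reproduces the consent form as it says it does, and that the unseen remainder of the form does not qualify the sentence. It should be corrected because it misstates a cardiac-risk disclosure to people the protocol knowingly admits.

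**What to change.** Delete the sentence from the RISKS section and from the consent form, or replace it with a conditional statement, for example:

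> If you are healthy and have no known risk factors for heart disease, your risk is expected to be lower than this. If you have high blood pressure or high cholesterol, or take medication for either, the lower risk may not apply to you.

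As an optional addition, staff can say the second sentence aloud when giving a participant high blood pressure or lipid results from the fasted visit, before circuit training starts. This covers people whose condition first comes to light after consent.

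The cost is a one-sentence wording amendment to the two documents and, if the option is taken, one spoken sentence at a point where results are already being given. Eligibility, sample size, procedures and analysis stay as they are.
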